3.3.2. The SEARCH Cohort Study

Cohort Study Follow-Up (Cohort Aims 1 and 2). A subset of SEARCH 3 Cohort (C_1) and SEARCH 3 Registry (R_1) participants will be invited for a SEARCH 4 in-person visit. The eligible group will include all SEARCH 3 (C₁ and R₁) participants with T2D, all minority youth with T1D, and a random sample of NHW youth with T1D. The Coordinating Center (CC) will provide a list of randomly selected NHW youth with T1D to be invited for participation such that all participants will be 10 years or older, have at least 3 years of time elapsed since their SEARCH 3 (C_1 or R_1) visit and have at least 5 years of duration of diabetes at the time of their planned SEARCH 4 IPV. NHW sampling is performed since based on the limited available budget it was determined that there was minimal gain in statistical power to invite all T1 NHW youth for a return visit and that all proposed analyses could be addressed with the random sample of NHW T1. Table 3 shows the total number of participants expected to complete a SEARCH 4 Cohort visit ($N \sim 1.846$) based on the proposed sampling. These estimates are based on an expected 75% response rate. In addition, the SEARCH 4 IPV will include a sample of 500 participants to be identified by the CC to have cardiac echocardiogram measurements taken. This sample will include 250 T1D and 250 T2D with representation from all five clinical sites and have racial/ethnic diversity.

The remainder of SEARCH 3 (C_1) participants will form the survey-only group with no IPV in SEARCH 4. The survey-only option will also be offered to individuals who are eligible but refuse participation in the IPV. The survey-only group will be asked to complete questionnaires by mail, phone or internet. Survey data will be combined from the IPV and survey-only participants (at least2,546) to address Aim 2.

Cohort Study, by Clinical Site							
Site	In-Person Visit	Echocardiogram	(Estimated) Survey Only				
Carolinas	434	140	150				
Ohio	298	130	150				
Colorado	504	130	225				
California	352	0	25				
Washington	258	50	150				
Total	1846	450	700				

Table 2. Number of Expected participants for each component of the SEARCH 4

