Retinal Photography. We will continue obtaining retinal images using Canon CR-1 Mark II fundus cameras. Consistent with NHANES protocol (46), two 45-degree images are taken of each eye: one centered on the optic nerve and the other on the fovea. The Ocular Epidemiology Reading Center at the University of Wisconsin-Madison (47) will grade the images for presence and severity of diabetic retinopathy (DR), macular edema and will make measurements of retinal vessel calibers. After grading the retinal images from the 2nd retinal visit, a separate longitudinal review will be conducted to confirm progression/regression status of diabetic retinopathy or macular edema severity.

Table 4. Data Collected on Cohort Study Participants						
Variables	Baseline Visit (C0)	12, 24, 60 months	SEARCH 3 Visit (C ₁)	SEARCH 4 Visit (C2)		
Surveys:						
Demographics: Sex, Race/ethnicity, Parental age	X					
Employment, education: parent or youth > 18 years		Х	X	Х		
Medical Record: Diabetes type, date of diagnosis	Х					
Health History: Birth date & weight, age at onset	Х					
Pubertal status, co-morbidities; family history	Х	Х	Х	Х		
Pregnancy outcomes in females				Х		
Medication: Diabetes & related conditions	Х	Х	Х	Х		
Behavioral: Diet, physical activity, alcohol use	Х	Х	Х	X		
Marijuana, other substance use				Х		
Processes of care/quality of care			Х	X		
Health care costs			Х	X		
Psychosocial: Depression (CES-D)	Х	Х	Х	Х		
Family conflict; fear of hypoglycemia			Х	X		
Transitions of care			Х	X		
Food security and assistance				X		
Stressors; work ability index; stigma/discrimination				Х		
Physical exam: BMI, waist , blood pressure, acanthosis	Х	Х	Х	X		
Laboratory measures (blood):				1		
Autoantibodies	X	X	X			
Fasting glucose, cystatin C, serum creatinine, fasting C-peptide, lipid profile, inflammatory markers (CRP, IL6), A1c, AGE (CML), DNA, miRNA extraction	Х	X	X	X		
URINE: albumin, creatinine (spot)	Х	Х	Х			
URINE: albumin, creatinine (first morning void)			Х	Х		
Stored Samples: DNA, miRNA, serum, plasma, urine	Х	Х	X	Х		
Outcome(s):			-			
Cardiovascular: Arterial stiffness (PWV, AiX)	Х		X	Х		
Cardiac echocardiography: LV mass, systolic & diastolic function				Х		
Neuropathy: heart rate variability; peripheral neuropathy		X (pilot)	X	Х		
Retinopathy Retinal photos, vessel caliber		X (pilot)	Х	Х		
Nephropathy: Albuminuria	Х	X	Х	Х		
Cystatin C		Х	Х	Х		
Neurocognitive tests: NIH Toolbox.				Х		
Acute complications: DKA, hypoglycemia	Х	Х	Х	Х		

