Quality of life (Peds QL3.2 Diabetes Module)	Х	Х	Х	Х		
Mortality surveillance (NDI)	Х	Х	Х	Х		

Measures of Kidney Function

Urine albumin:creatinine ratio: We will collect first morning void (FMV) urine samples for storage and calculation of urine albumin:creatinine ratio (UACR). We will request a second FMV sample in the case of a positive urine for microalbuminuria (UACR \geq 30µg/mg), or if a urine sample is rejected due to possible contamination (positive leukocyte esterase and/or nitrite). In previous phases we had collected random urine samples (with the addition of the FMV at SEARCH 3).

Estimated glomerular filtration rate: Equations with the most accurate and precise estimation of glomerular filtration rate (GFR), utilize both serum creatinine and cystatin C (48, 49). Both tests have been measured in SEARCH 1-3 and continue to be measured in SEARCH 4. Different equations are currently used in children versus adults, and on the expected range of GFR (hyperfiltration versus normal GFR versus low GFR) (48-51). The natural history of eGFR in diabetic kidney disease can be heterogeneous and so we will also investigate the optimal equations for use in children versus adults and at different spectrums of GFR.

Measures of Neuropathy

Peripheral Neuropathy: The Michigan Neuropathy Screening Instrument (MNSI) will be used to screen for the presence of diabetic neuropathy. It consists of 15 self-administered questions on foot sensation including pain, numbress and temperature sensitivity. The second part of the MNSI is a brief physical examination involving 1) inspection of the feet for deformities, dry skin, hair or nail abnormalities, callous or infection, 2) semiquantitative assessment of vibration sensation at the dorsum of the great toe, 3) grading of ankle reflexes and 4) monofilament testing. Patients screening positive on the clinical portion of the MNSI (greater than 2 points on a 10 point scale) are considered neuropathic.

Cardiac Autonomic Neuropathy: Heart rate variability (HRV) analysis allows us to assess the autonomic nervous system by examining sympathetic balance, which raises heart rate and blood pressure and causes vasoconstriction, and the parasympathetic balance which has opposite effects (52,53). Assessments use a SphygmoCor SCOR-CPV device (AtCor Medical, Australia) as performed previously (54).

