6.2. COHORT STUDY - STATISTICAL CONSIDERATIONS

6.2.1. Aim 1: Burden of Complications

Three main analytic approaches will be employed to examine the prevalence, incidence, progression and clustering of complications by diabetes type and responsible risk factors and pathways: a) estimating incidence and prevalence using multiple logistic regression methods; b) estimating the progression of complications using longitudinal mixed models; and c) estimating the clustering of risk factors and outcomes using longitudinal mixed models. For each of these approaches we will incorporate participant level characteristics, measured at multiple time points, to examine potential mediators and moderators of outcomes.

Incidence Rate Estimation: Participants have had at least two previous in-person visits (C_0, C_1) ; however, for many outcomes (retinopathy, neuropathy, etc.) participants will have had only one previous assessment (C1 visit). For these outcomes we will be able to define a group of participants who were free from the event of interest (e.g. no retinopathy) at C1. Multiple logistic regression methods will be employed to examine the incidence rates of binary measures, with categorical (e.g.T1D vs. T2D) or continuous (e.g. A1c) predictors. We will evaluate potential confounding and/or effect modification based on our extensive databases.

Prevalence Rate Estimation: Some of the outcomes of interest have not been measured previously (e.g. echocardiography); therefore, we will estimate the prevalence of these outcomes. Associations of risk factors and diabetes type with prevalent outcomes will be examined using logistic regression models.

Statistical Power: For each of the primary dichotomous outcomes of interest (incidence or prevalence) we estimated proportions that will have the specific outcomes of interest, based on data from the C₁ visit. Table 6 shows the expected sample sizes available for comparing T1D and T2D, the corresponding detectable differences in rates, and the power for each outcome. We also provide the expected detectable differences in prevalence rates of LV hypertrophy between T1D and T2D in the sample of patients receiving echocardiography. These calculations are performed using Fisher's exact tests with $\alpha = 0.05$ (2-sided).

Table 6. Power for detectable differences for primary outcomes								
Outcome	T1D/T2D available	T1D rate	T2D rate	Power				
	Incidence Comparisons							
Retinopathy	1215/230	10%	18%	88%				

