Neuropathy	1344/283	5%	10%	81%				
Nephropathy	1172/268	20%	29%	85%				
Prevalence Comparisons (Cardiac echocardiography)								
LV hypertrophy	250/250	5%	13%	86%				

Longitudinal Models: We will use a longitudinal mixed effects analysis of covariance approach to make comparisons among groups which includes duration of diabetes as a time-varying covariate and participant as a random effect. This approach models the varying durations of disease prior to the initial visit, and the varying durations of time allowed by the data collection windows between visits. These mixed effects models are flexible to allow for non-linear relationships to be modeled over time, and permit random rates of progression.

To estimate the sample size needed to detect a significant difference with sufficient power, calculations were based on comparing measurements after adjusting for C_0 or C_1 data. If the correlation between measurements is moderate (0.50) then we have 80% power to detect a difference of 0.139 standard deviations (SD) for each outcome of interest. For example, based on data collected on a subset of SEARCH T1D participants, the standard deviation for PWV carotid-femoral was estimated to be 0.7 m/s, thus we would have 80% power to detect a difference of 0.10 m/s in progression of PWV between youth with T2D vs T1D.

Clustering of Outcomes: In addition to examining each endpoint separately, we have the opportunity to look simultaneously at several outcomes in the same analysis. We

will create variables that describe the co-occurrence (clustering) of outcomes for each participant and examine whether there are differences in the patterns of these clusters between T1D and T2D youth. Approaches will utilize ordinal logistic regression methods or longitudinal mixed models depending on whether the clustering outcome is a count or categorical. More sophisticated statistical methods may also be used such as principal components analyses to determine which risk factors may form different components.

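### Incident neuropathy is one unconfirmed crossing of the MNSI cut after a negative C1 exam, so exam error counts as onset, more often in the diabetes type with higher C1 prevalence

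*Protocol*

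**What the plan says.** The case rule is in Protocol section 4.2, under Measures of Neuropathy: "Patients screening positive on the clinical portion of the MNSI (greater than 2 points on a 10 point scale) are considered neuropathic". It refers to one examination with a screening instrument.

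The at-risk set is in section 6.2.1, under Incidence Rate Estimation. For outcomes such as retinopathy and neuropathy that have only C1 as an earlier assessment, the analysis will "define a group of participants who were free from the event of interest (e.g. no retinopathy) at C1". Incidence is then compared by multiple logistic regression. Table 6 plans the neuropathy comparison with 1344 T1D and 283 T2D participants at risk, 5% against 10%, and 81% power. On method it says: "These calculations are performed using Fisher's exact tests with" a two-sided alpha of 0.05.

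The other two incidence outcomes have a safeguard at measurement. For the eye, "a separate longitudinal review will be conducted to confirm progression/regression status of diabetic retinopathy". For the kidney, section 4.2 asks for a second first-morning urine sample after a positive albumin:creatinine ratio. Nothing comparable is stated for peripheral neuropathy.

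Hypothesis 1.1 in section 2.2 expects higher incidence of chronic complications in T2D than in T1D.

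**The concern.** If the same cut defines both freedom from neuropathy at C1 and onset at C2, the count sees movement in one direction only. A participant at 2 points who scores 2.5 at the next visit becomes a new case. A participant at 2.5 who scores 2 is outside the at-risk set and is never counted. Error in grading reflexes, vibration or monofilament response then adds cases and removes none.

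The error need not be balanced between types. With equal exam quality, the type with more positives at C1 also has more participants just under the cut, or more true cases missed at C1, and so yields more false onsets. If that type is T2D, the bias runs in the direction of hypothesis 1.1. At stake is whether a significant difference in new cases can be read as higher true incidence in T2D.

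**Working it through.** **Inputs.** Table 6: 1344 T1D and 283 T2D at risk, 5% vs 10%, power 81%. Section 3.3.2: 1846 expected in-person visits. Section 6.2.2: 382 T2D. Section 6.2.1: detectable difference 0.139 SD at correlation 0.50 and 80% power. The protocol gives no exam reliability, error rate or C1 prevalence of neuropathy, so these are assumed below.

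**1. The plan's own power.** Pooled rate = (1344×0.05 + 283×0.10)/1627 = 0.0587. SE under no difference = √[0.0587×0.9413×(1/1344 + 1/283)] = 0.0154. SE under the planned rates = √(0.0475/1344 + 0.09/283) = 0.0188. Continuity correction = ½(1/1344 + 1/283) = 0.0021. Power = Φ[(0.05 − 0.0021 − 1.96×0.0154)/0.0188] = 82.7%. Using the unweighted mean rate without the correction gives 80.6%; full enumeration of Fisher's test gives 84.1%. The stated 81% is sound.

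**2. Size of the two groups.** 1846 − 382 = 1464 T1D. Check: 2.8016 × √(1 − 0.5²) × √(1/1464 + 1/382) = 0.1394, which matches the stated 0.139.

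**3. Upper limit for C1 prevalence.** T1D: (1464 − 1344)/1464 = 120/1464 = 8.2%. T2D: (382 − 283)/382 = 99/382 = 25.9%. This treats everyone not at risk as C1-positive.

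**4. False onsets when nobody truly changes.**

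Model A: normal scores with test-retest correlation r and C1-positive share p. With c = Φ⁻¹(1 − p), false onset = [(1 − p) − Φ₂(c, c; r)]/(1 − p).

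Model B: fixed sensitivity (se) and specificity (sp), errors independent between visits. True prevalence π = (p − 1 + sp)/(se + sp − 1), and false onset = [π(1 − se)se + (1 − π)sp(1 − sp)]/(1 − p).

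| Assumption, shares 8.2%/25.9% | T1D | T2D | Difference (points) | Fisher p<0.05 |
|---|---|---|---|---|
| A, r = 0.95 | 2.1% | 5.5% | 3.5 | 81% |
| A, r = 0.90 | 2.9% | 7.8% | 4.9 | 93% |
| A, r = 0.80 | 4.1% | 11.1% | 7.0 | 99% |
| B, se 0.95, sp 0.99 | 1.4% | 2.7% | 1.3 | 31% |
| B, se 0.90, sp 0.98 | 2.7% | 5.2% | 2.6 | 54% |
| B, se 0.80, sp 0.95 | 5.7% | 10.6% | 5.0 | 80% |

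With equal C1 shares (10%/10%) the difference is 0 at every r.

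**5. If part of the shortfall had no C1 exam.** Section 3.3.2 also invites participants from the SEARCH 3 registry visit, and the number without a C1 neuropathy exam is not given. The splits below are illustrative; all keep 1344/283 at risk and use model A at r = 0.90. Prevalence is (120 − a)/(1464 − a) for T1D and (99 − b)/(382 − b) for T2D.

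| Without C1 exam (a T1D / b T2D) | C1 prevalence | False onset | Fisher p<0.05 |
|---|---|---|---|
| 40 / 60 | 5.6% / 12.1% | 2.1% vs 4.1% | 43% |
| 20 / 70 | 6.9% / 9.3% | 2.5% vs 3.3% | 10% |
| 30 / 80 | 6.3% / 6.3% | 2.3% vs 2.3% | 4% |

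**6. What would reduce it.** Under model A with the 8.2%/25.9% shares and r = 0.95 to 0.80, a confirming second exam still leaves 1.7 to 3.3 points. A minimum rise of 1.96 standard errors of a difference leaves about 0.5 to 1.0. Comparing mean score change in everyone examined twice has expectation zero under no change, whatever the C1 prevalence; in simulation it rejected in 4 to 5% of studies.

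**The case against.** The strongest objection concerns size. A reader might infer that exam noise alone would reproduce the planned 5% vs 10%, and that a false positive finding is near certain. The documents do not support that. It needs the full shortfall to be C1 neuropathy and an exam reliability near 0.90 (or a chosen error pair such as se 0.80, sp 0.95), and the protocol states neither. Step 5 shows that the same counts fit no false difference at all.

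The rejection percentages are for an unadjusted Fisher test, which section 6.2.1 uses for power only. The planned analysis is logistic regression with confounding evaluated, and hypothesis 1.1 is framed as independent of age, sex, duration and race/ethnicity. Adjustment does not correct exam error, but the false difference would shrink if those covariates explain the C1 gap. The percentages cannot be carried over to the planned model.

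Section 6.2.1 also already plans longitudinal mixed models for progression. Staff are trained and certified, which limits exam error without removing it. The derivation of an incident case may be detailed in an analysis plan not at hand, and use of the same cut at C1 is the natural reading of sections 4.2 and 6.2.1 rather than an explicit statement.

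A reader might also infer that the 81% power is wrong. It is not; step 1 reproduces it.

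These points limit the size and leave the mechanism standing. The case rule, at-risk set and comparison are all fixed in the protocol, and it does not say that the score analysis will guard the reading of the incidence count.

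**Conclusion.** The point holds as a bias of uncertain size. As sections 4.2 and 6.2.1 read, incident neuropathy is a single upward crossing with no stated confirmation or minimum change, so exam error produces false onsets and produces more of them in the type with higher C1 prevalence.

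At the upper-limit shares of 8.2% and 25.9%, with no true change and assumed reliability 0.95 to 0.80, the false difference is about 3.5 to 7 points against the planned 5. With sensitivity 0.95 and specificity 0.99 it is about 1.3 points. With equal C1 prevalence it is zero. These figures rest on the assumed error models, the inferred 1464/382 split and the same cut at both visits. A significant difference in the count alone is therefore not secure evidence of higher true incidence in T2D.

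**What to change.** Keep the incidence count and its 81% power. In section 6.2.1:

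- State that the T1D-T2D neuropathy comparison will also be made on the 0-10 MNSI exam score, in all participants examined at both C1 and C2, without conditioning on C1 status, using the longitudinal mixed model already planned with a diabetes type × time term.
- Report C1-positive to C2-negative reversions by type beside the new cases.
- State that a difference in the threshold count will not be read as higher true incidence in T2D unless the score analysis agrees.
- State whether the C1 status uses the same cut, and how many in-person participants of each type have no C1 neuropathy exam.

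A two-state model with misclassification is at most a sensitivity analysis. Two visits give three free proportions per type, fewer than prevalence, onset, sensitivity and specificity together, so its assumptions (for example no true remission and equal error in both types) must be stated.

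The cost is one more analysis and a more cautious incidence conclusion. Both exams are already in Table 4, so no new data are needed.

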5.1. PROJECT #1: CASE ASCERTAINMENT BY DIABETES TYPE

The goal of D&V Project 1 is to maximize the automation of ascertainment of diabetes cases, overall and by diabetes type, by applying case identification algorithms and text analytics/natural language processing (NLP). This work is critical to Tier 1 (Prevalence) efforts. Two approaches will be employed building on previously described SEARCH work (17, 60) one based on algorithms using EHR and administrative data, the second using natural language programming (NLP) to extract and analyze text. We will attempt to replicate our previous work using EHR-based algorithms as developed in the Carolinas site to determine if these algorithms perform in a similar manner in an integrated health care system in the California site. Additionally, we will apply case identification algorithms to the PEDSnet data for the three SEARCH sites, and compare results to those using the SEARCH gold standard methods using metrics described above. Regarding the text analytics approaches, we propose to apply work as developed in the Carolinas site, including re-training of the machine learning models, to clinical notes from at least one provider from each of the five SEARCH centers, to include the three SEARCH centers that are part of PEDSnet, the CA center utilizing the KPSC data systems and Carolina working with HSSC.

5.2. PROJECT #2: DETERMINATION OF DIAGNOSIS DATE

The critical information element that distinguishes Tier 1 (Prevalence) surveillance from Tier 2 (Incidence) surveillance is date of diagnosis, which generally is not available as a structured data element that can be easily extracted from the EHR. Thus, the current literature that describes various EHR-based algorithms for case identification is generally applicable only to prevalence. The goal of D&V Project # 2 is to use electronic ascertainment methods to determine diabetes diagnosis date with an expectation that at least 95% of the estimated dates will identify the correct calendar year of diagnosis. As in D&V Project #1, two approaches will be employed: 1) use of EHR-based algorithms applied to structured data; 2) use of text analytics applied to unstructured data.

All five SEARCH centers will participate in the EHR-based algorithm work. Regarding use of text analytics, the Carolinas site will continue to refine the machine learning model with the goal of attaining at least 90% accuracy for year of diagnosis. Once optimal algorithms are established for T1 and T2D, we will expand the effort to build on the text analytic work being done for D&V Project # 1 at each of the five SEARCH centers.

5.3. PROJECT #3: AUTOMATION OF CARE AND CLINICAL DATA COLLECTION

The third project will focus on whether the collection of core and selected demographic and clinical information can be automated by directly importing information from the EHR and other clinical and administrative data systems. In addition to data obtained as part of case ascertainment by diabetes type (Project #1, Tier 1) and date of diagnosis (Project # 2, Tier 2), additional information of importance includes race and ethnicity, measurement of diabetes autoantibodies, clinical information including laboratory values related to diabetic

ketoacidosis, diabetes medications, etc. The evaluation of the data capture procedures will consider both completeness as well as the accuracy of the information extracted compared to manual extraction of core data.

5.4. PROJECT #4: EXPANSION OF SURVEILLANCE TO ADDITIONAL AMERICAN INDIAN (AI) TRIBES

Since its inception in 2000, SEARCH has been conducting surveillance of youth onset diabetes in AI tribes under the direction of the Colorado site. These results indicate that AI youth have the highest incidence and prevalence of T2D of any major race/ethnic group (61, 6, 9). Unfortunately, the AI population under surveillance is the smallest of the major race/ethnic groups (~95,000 youth), and results in less than ~40 incident cases per year across all sites. The goal of this project is to develop and validate an algorithm that may be used to identify AI and possibly Alaskan Native (AN) youth with diabetes using data extracts from *existing* electronic health records (EHR) of the Indian Health Service (IHS). For the proposed pilot project, the SEARCH Colorado site will partner with the Center for AI AN Health (CAIANH), both located within the Colorado School of Public Health.

An algorithm will be developed to identify AI youth aged < 20 years with diabetes using IHS data that includes diagnostic codes, provider and service type information and dispensed medications. The algorithm will be developed from the IHS data for the Chinle and Tuba City Service Units on the Navajo Reservation and validated by comparison to the Navajo SEARCH registry (gold standard) for the same service units and will result in metrics for sensitivity, specificity, positive and negative predictive value. Next, and coordinated through CAIANH, the best algorithm developed in Phase 1 will be used to identify AI youth with diabetes in another IHS Service Unit, from a different tribe, using the same IHS National Data Warehouse.

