3.1. STUDY SITES

The five clinical centers that participated in SEARCH 3 will continue their participation in SEARCH 4. These sites are based in Ohio, Colorado, Washington, South Carolina, and California. Four SEARCH centers (Ohio, Colorado, Washington, and South Carolina) are geographically based - that is, newly diagnosed diabetes cases are identified from a geographically defined population. One SEARCH center (California) is membership-based - that is, newly diagnosed diabetes cases are identified from the participating health plan. Each of the five centers participates in both the Registry and the Cohort Studies.

- 1. Ohio Cases ascertained from Cincinnati and the 8 surrounding counties; oversight, recruitment and clinic visits provided by Children's Hospital Medical Center.
- 2. Colorado Cases ascertained from the state of Colorado and members of the Navajo Indian tribe in AZ, UT, or NM residing on the Navajo Nation reservation; oversight, recruitment and clinic visits provided by University of Colorado, Denver.
- 3. Washington Cases ascertained from Seattle and Tacoma and the 5 surrounding counties; oversight, recruitment and clinic visits provided by Seattle Children's Research Institute.
- 4. Carolinas Cases ascertained from the state of South Carolina with oversight provided by the University of North Carolina at Chapel Hill. Sub-centers are located at three locations in SC (Charleston, Greenville, Columbia) to assist with recruitment and clinic visits.
- 5. California Cases ascertained from Kaiser Permanente Southern California Health Care Plan membership (other than San Diego) with oversight, recruitment and clinical visits provided by the same.

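### The pilot American Indian case-finding algorithm has no stated validation data separate from its development units, so its Navajo accuracy figures are likely somewhat optimistic and say little about another tribe's unit

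*Protocol*

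**What the plan says.** Protocol section 5.4 (Project #4) sets out a pilot in two stages.

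- **Development:** "The algorithm will be developed from the IHS data for the Chinle and Tuba City Service Units on the Navajo Reservation".
- **Validation:** the algorithm is "validated by comparison to the Navajo SEARCH registry (gold standard) for the same service units". This step "will result in metrics for sensitivity, specificity, positive and negative predictive value". No numerical target is given.
- **Carrying forward:** "the best algorithm developed in Phase 1 will be used to identify AI youth with diabetes in another IHS Service Unit, from a different tribe". Data for that second unit come from the IHS warehouse that also serves the Navajo units. No registry comparison or other reference check is described for it.

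The opening of section 5 gives a general three-step process for all the development and validation projects. Step 1 is initial validation in limited locations. Step 2 is further validation at additional SEARCH centers. Step 3 allows implementation in Registry work only after pre-determined metrics have been shown for each electronic health record (EHR) system. Section 5.4 does not say how these steps apply to a service unit of another tribe.

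**The concern.** Choosing the best algorithm implies at least two candidates, and the registry comparison is the only evaluation described in section 5.4. If the winner is picked on that comparison and its metrics are reported from the same comparison, the figures carry selection optimism. If rules or cut-offs are also tuned against the registry, fitting optimism is added.

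The protocol is more careful elsewhere. In section 5.1, EHR-based algorithms developed at the Carolinas site are tried in California, and algorithms run on PEDSnet data are compared with the SEARCH gold standard. Project #4 moves its algorithm to a different tribe, yet describes no comparable check.

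What is at stake is modest but real. Section 6.1.2 gives the limited power in American Indian and Asian/Pacific Islander youth as the reason for this project, so the pilot's metrics would inform whether the approach is extended. Overstated sensitivity would make case finding look more complete than it is.

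**Working it through.** **1. Text.** The development units and the validation units are the same two, Chinle and Tuba City. No held-out unit, year or subsample is named. The step in the second unit is use, not validation.

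**2. Do the general steps of section 5 settle it?** Not clearly.

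- Step 2 concerns additional SEARCH centers. Another tribe's IHS unit is not described as one. The only tribal population named in section 3.1 is "members of the Navajo Indian tribe in AZ, UT, or NM residing on the Navajo Nation reservation".
- Step 3 works per EHR system. The second unit draws on the same IHS warehouse, so the Navajo results could be read as already satisfying the rule.

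**3. Size of the possible optimism.** The protocol states no accuracy figure, number of candidates or number of validation cases for Project #4, so there is nothing to reproduce. The bias was sized by simulation (3,000 runs per setting). Every input is an assumption:

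- K candidates (1, 5 or 20), with true sensitivity of mean 90% and SD 2 points, and true specificity of mean 95% and SD 1 point.
- All candidates are scored on the same people, with correlation 0.5 or 0.8 between their errors.
- 40, 100 or 200 gold-standard cases, with 3 non-cases per case.
- The candidate with the highest apparent sensitivity plus specificity is chosen.
- Optimism = apparent sensitivity of the chosen candidate − its true sensitivity.

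Mean optimism in sensitivity, in percentage points (range over the two correlations):

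| Gold-standard cases | K = 1 | K = 5 | K = 20 |
|---|---|---|---|
| 40 | −0.1 to 0.1 | 2.7 to 3.5 | 4.1 to 5.3 |
| 100 | −0.1 to 0.0 | 1.4 to 2.0 | 2.2 to 3.0 |
| 200 | −0.1 to 0.1 | 0.9 to 1.2 | 1.3 to 1.8 |

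The range with selection is therefore 0.9 to 5.3 points, or about 1 to 5. The K = 1 column shows that the bias comes from selection: without it, the mean error is about zero. Tuning of rules to the registry is not modelled and would add to these figures.

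**4. Scale against sampling error.** The 95% Wilson interval around an observed sensitivity of 90% is 77% to 96% with 40 cases, 83% to 94% with 100, and 85% to 93% with 200. The optimism is smaller than the width of the interval, but it is systematic, and the interval does not show it.

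**5. Transport to another tribe.** PPV = sens × prev / [sens × prev + (1 − spec) × (1 − prev)]. For illustration, assume sensitivity 90% and specificity 99.9%:

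- Prevalence 1 per 1,000: 0.0009 / (0.0009 + 0.000999) = 47%.
- Prevalence 2 per 1,000: 0.0018 / (0.0018 + 0.000998) = 64%.
- Prevalence 4 per 1,000: 0.0036 / (0.0036 + 0.000996) = 78%.

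Even with sensitivity and specificity unchanged, predictive value moves with prevalence, and it can move either way. The Navajo values therefore give no known direction of error for the new unit.

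**The case against.** The case on the other side has force in several places.

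- **Matching units may be geographic only.** A registry can validate an algorithm only where it has ascertained cases. The text does not say that the same records or years serve both steps, and a split by person or year is not excluded. Rules written from IHS codes and medications without reference to the registry would carry no fitting bias. This stands, and it is why the conclusion is conditional. Selection among candidates still remains if the best is chosen on the registry comparison.
- **Resampling detail may belong in an analysis plan.** This stands in part. The protocol does, however, fix the validation units itself, and they are the development units.
- **This is a pilot, and section 5 calls the first validation initial.** This stands and keeps the point minor. Nothing in section 6.1 places counts from the new tribe into an Aim 1 to 3 estimate.

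A reader might also infer more than the protocol supports:

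- **That accuracy in the new tribe's unit will be overstated.** The absence of a described reference check leaves accuracy there unknown. It gives no direction.
- **That no gold standard can exist there.** Section 5.4 does not identify the unit, so whether registry data cover it cannot be determined.
- **That the validation sample is about 40 cases.** The statement that the population under surveillance "results in less than ~40 incident cases per year across all sites" is a yearly incident count. The algorithm finds youth under 20 with diabetes, which may include prevalent cases, and the gold-standard count for the two units is not given.
- **That the bias is larger, about 3 to 7 points.** A best-of-10 simulation gives 2.7 to 6.7 points with 60 to 200 cases. It takes candidates of identical true sensitivity (85%), chosen on sensitivity alone, with correlation from 0 to 0.8. Identical candidates maximise the winner's advantage, and rules built from the same codes will hardly be uncorrelated. The 1 to 5 point range is the safer one.

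**Conclusion.** The point holds as a minor, inexpensive improvement. Section 5.4 develops and validates in the same two service units, carries forward the best algorithm and names no held-out data. If candidates are tuned or chosen on the registry comparison, the Phase 1 metrics are apparent accuracy and likely somewhat optimistic, by roughly 1 to 5 points of sensitivity. That size depends on the assumed 5 to 20 candidates, 40 to 200 gold-standard cases and error correlation of 0.5 to 0.8. It shrinks to about zero with a single candidate or independent test data.

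Accuracy in the other tribe's unit is unknown on the protocol as written. The protocol does not support a claim that optimism is certain, or that it carries over to the new unit in a known direction.

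**What to change.** Change section 5.4 so that the Phase 1 metrics come from data not used to develop or select the algorithm. Either route uses data already planned:

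- develop in one service unit, test in the other, then swap; or
- pool the two units and use cross-validation or the bootstrap, repeating the choice of algorithm inside each fold or resample.

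Report these held-out metrics as the Phase 1 result. The algorithm carried forward may still be built on both units. The held-out figures then describe the procedure that produced it.

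Add a sentence that the Navajo metrics are not presented as the algorithm's accuracy in the new tribe's unit, and say how the three steps of section 5 apply there. Resampling Navajo data cannot supply accuracy for another tribe. That would need a reference check in the new unit, such as chart review of a sample, which is a separate decision with its own cost.

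The main change costs a little more analysis and gives slightly lower and less precise reported metrics.
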